accountability												
Criteria for dose reduction/ interruption check	X		X		X		X		X			
			X				X		X/Q24w		X	
			X				X		X/Q24w		X	
	X		X		X		X		X		X	
	X		X		X		X		X		X	X
	X		X		X		X		X		X	X
Bone imaging (if applicable) ²¹	ON REGULAR BASIS (Q12W to Q48W) ²¹										X ²⁴	
Dental examination ²²	ON REGULAR BASIS (Q12W to Q24W) ²²										X ²⁴	
Dental imaging ²³	ON REGULAR BASIS (Q24W to Q48W) ²³										X ²⁴	
All AEs/ SAEs/AESIs	X		X		X		X		X		X	X ²⁷
Concomitant therapy	X		X		X		X		X		X	X
Vital status data ²⁵			(X) ²⁵				(X) ²⁵		X/Q24w			(X) ²⁵
Completion of patient participation ²⁸							(X) ²⁸		(X/Q24) ²⁸			X ²⁸

1. **For new patients**, the interval between Visit 1 and Visit 2 should be ≤ 28 days. The interval between Visit 1 and Visit 2 could be >28 days in case the assessments required to check inclusion and exclusion criteria cannot be completed within 28 days (e.g. in case the available HRCT scan fails to meet the required image acquisition specification, laboratory test results show out-of-range values requiring retest, etc.) but the screening period (from informed consent signature to Visit 2) must not be longer than 12 weeks.

For roll-over patients, Visit 1 and Visit 2 should occur the same day as EoT in InPedILD[®] 1199-0337 trial. In this case, all common procedures (e.g. physical examination, vital signs, height, leg length, weight, pregnancy test, ECG, ██████, spirometry and some laboratory tests) will be performed once. If a patient is unable to roll-over on the day of EoT in 1199-0337 InPedILD[®] due to medical reason or in case the site is not ready to be initiated, the patient can be permitted to roll-over within 8 weeks following EoT. The interval between EoT and Visit1/Visit 2 or Visit 1 and Visit 2 may be extended at the discretion of Sponsor on a case-by-case basis.

2. Weeks and Days from the Day 1 (day of Visit 2).

3. During treatment period:

- Intermediate lab tests (“a” Visit) will be done as needed for additional safety monitoring at the discretion of the investigator, or as recommended by the Safety Monitoring Committee (SMC). Blood and urine sampling may be collected at the investigational site, primary care physician (GP, Pediatrician or Pulmonologist) or external laboratory preferably with specific study kits sent to the central laboratory for analysis or analysed locally.

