From Visit 2 for roll-over patients ≥ 26 weeks and from Visit 3 for new patients and for roll-over patients < 26 weeks, urine dipstick pregnancy tests will be provided with pregnancy test diary card when needed. Use of pregnancy test diary card will be explained with the patient / parent(s)/legal guardian and training will be repeated as needed. The pregnancy test diary card will be used to support the record of the date and result of test(s) between consecutive visits. Pregnancy test diary card will be reviewed at clinic visits. In case a positive test is reported the sponsor should be contacted immediately. Refer to [Section 3.3.4.1](#) for further instructions. Refer to [Section 5.2.7.2.3](#) for detailed information on event reporting in case of pregnancy.
14. [REDACTED]
15. **For new patients:** Order of lung function measurements: 1. FVC followed by patient's rest; 2. DLCO.
For roll-over patients, DLCO not applicable.
For all patients: after Visit 2 FVC measurements to be done at the same time each visit (+/- 90 min), with reference time at Visit 2.
16. [REDACTED]
17. Interactive Response Technology (IRT) should be notified upon obtaining informed consent.

18.

Please refer to [Appendix 10.1](#) for details.

19.

20.

21. Bone imaging. Please refer to [Section 5.2.5](#) and to the image acquisition guideline available in the ISF for details. For patients aged 19 and older, please see additional information at the end of the footnote.

For new patients: Bone imaging is required for all new patients who qualified for assignment of nintedanib treatment at Visit 2 as baseline. If it's not possible to conduct the baseline bone imaging at Visit 2, the procedure can be done in the 2 weeks immediately after the visit (until D15).

Imaging follow-up will be conducted only in patients with open physes at predefined time points. Imaging follow-up will be conducted, if applicable, at 12 weeks, 24 weeks, 36 weeks, 52 weeks, 76 weeks, 104 weeks, 128 weeks, 156 weeks, and every 24 weeks thereafter until the end of study or closure of the physes. If it's not possible to conduct the follow-up at the predefined time points, the procedure can be done within 1 week before and after this time point with always minimum of 10 weeks (during the first year)/22 weeks (thereafter) and always maximum of 16 weeks (during the first year)/28 weeks (thereafter) between 2 procedures.

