For roll-over patients: Bone imaging procedure is not applicable for patients with closed physes at the end of InPedILD[®]. For all other roll-over patients, previous MRIs/x-rays of epiphyseal growth plates within 12 weeks (for roll-over patients with treatment duration less than 52 weeks in InPedILD[®]) and within 24 weeks (for roll-over patients with treatment duration more than 52 weeks in InPedILD[®]) prior Visit 2 should be used as baseline in the analyses of bone imaging (for scheduling of follow-up procedures see next paragraph). If a previous MRI/x-ray as outlined above, is not available, an MRI/x-ray should be conducted at Visit 2. If it's not possible to conduct it at Visit 2, the procedure can be done in the 2 weeks immediately after the visit (until D15).

Irrespective of scheduled visits, imaging follow-up will be conducted only in patients with open physes, every 12 weeks in the year after the start of the trial medication in the parent trial (when applicable) and every 24 weeks thereafter until the end of the study or closure of the physes.

If it's not possible to conduct the follow-up at the predefined time points, the procedure can be done within 2 weeks before and 4 weeks after this time point with always a minimum of 10 weeks (during the first year after the start of the trial medication in the parent trial)/22 weeks (thereafter) and always a maximum of 16 weeks (during the first year after the start of the trial medication in the parent trial)/28 weeks (thereafter) between 2 procedures.

Preponement or postponement of one follow-up procedure by 2 months to the planned timepoint will be allowed once to align this procedure and the subsequent ones with the regular clinic visits planned in the protocol. After this alignment, the acceptable time window will be +/-1 week for this procedure (as for new patients).

For patients aged 19 and older, bone imaging follow-up procedures will be performed around every 48 weeks (instead of around every 24 weeks) until the end of the study or closure of the physes.

For all patients, if the follow-up procedure cannot be conducted at least every 16 weeks (during the first year)/28 weeks (thereafter), the study treatment of this individual patient needs to be interrupted upon discussion with the sponsor (except for the one-time alignment with clinic visits mentioned above for roll-over patients).

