	
bones (femur and tibia). Changes seen in rodents were: in epiphyseal growth plates (thickening due to increased number of hypertrophic chondrocytes) and articular cartilage (swelling of chondrocytes in the basal layers). These changes were reported during bone growth and were reversible after discontinuation.
	
Regular evaluation by radiology expert, with skeletal growth monitoring (MRIs or x-rays of epiphyseal growth plates) at baseline and regular follow-up conducted in patients with open physes at predefined time points until end of the study or closure of the physes (defined as 100% skeletal maturity) in patients with open physes. The follow-up bone imagings will be planned, irrespective of scheduled visits, in order to respect the frequency of around every 12 weeks for first year and around every 24 weeks thereafter, taking in account, for roll-over patients, the participation in the parent trial. Please refer to Flow Chart footnotes and to CTP Section 5.2.5 for more details. Expedited reporting of pathological findings identified on bone imaging (AESI).
 
Regular evaluation by SMC.
 
Not applicable for roll-over patients with closed physes at the end of parent trial

Impact on dentition	
In animal models, nintedanib has been shown to impact tooth development. Tooth changes were major with altered tooth structure and function which were irreversible. (In rodents (more prominently in the rat than in the mouse), nintedanib induced a pharmacologically mediated dentopathy
	
Monitor potential severe/irreversible effects on dentition by:
 
Regular evaluation by dentist, with dental examination at baseline and regular follow-up conducted at predefined time points. The follow-up dental examinations will be planned, irrespective of scheduled visits, in order to respect the frequency of around every 12 weeks for first year and around every 24

Potential risks of clinical relevance for this trial	Summary of data, rationale for the risk	Mitigation strategy

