5.2.5 Assessment of pathological findings of epiphyseal growth plate

MRI assessments of the distal femur and proximal tibia will be conducted as primary bone imaging methodology to assess the potential risk of skeletal toxicity of nintedanib in the growing population. In each patient the same side should be imaged at each assessment. In situations in which MRI cannot be performed, especially if sedation is required, x-rays of the distal femur and proximal tibia (AP knee radiograph) will be conducted as secondary methodology. For roll-over patients, the procedure followed to make these measurements for a given patient must be consistent with the procedure followed in the parent trial.

MRIs/x-rays of growth plates will be conducted in all patients who qualified for assignment of nintedanib treatment at Visit 2 (baseline) except in roll-over patients with closed physes at

the end of parent trial and patients that had previous MRIs or x-rays in the time window described below.

Imaging follow-ups will be conducted only in patients with open physes, at pre-defined time points until end of the study or closure of physes.

The follow-up will be planned, irrespective of scheduled visits, in order to respect the frequency of around every 12 weeks for first year and around every 24 weeks thereafter, taking in account, for roll-over patients, the participation in the parent trial with always minimum 10 weeks (first year)/22 weeks (thereafter) and always maximum 16 weeks (first year)/28 weeks (thereafter) from previous procedure. For patients aged 19 and older, bone imaging follow-up procedures will be performed around every 48 weeks (instead of around every 24 weeks) until the end of the study or closure of the physes.

Please refer to [Flow Chart](#) footnotes for more details. Timepoints may be adapted on a case-by-case basis after discussion with the sponsor if appropriate for patient's safety. Previous MRIs or x-rays of epiphyseal growth plates within respectively 12 weeks (for the first year) or 24 weeks (after the first year) prior baseline should be used at baseline for patients previously involved in InPedILD[®] with respectively less or more than 52 weeks in InPedILD[®].

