- The next visit will be scheduled; patient/parent(s)/legal guardian will be instructed on procedures to be followed until the next visit.

Procedures to be conducted at predefined time points, irrespective of scheduled visits, according to time window defined in the [Flow Chart](#). If it is not possible to conduct the follow-up at the predefined time points, please refer also to footnotes 21, 22, and 23 in the [Flow Chart](#).

- Follow-up bone imaging (MRIs or x-rays if baseline MRI was not possible) will be planned, in order to follow the frequency of around every 12 weeks for first year and around every 24 weeks thereafter, taking in account, for roll-over patients, the participation in the parent trial:
 - **For new patients**, imaging follow-up will be conducted, if applicable, at 12 weeks, 24 weeks, 36 weeks, 52 weeks, 76 weeks, 104 weeks, 128 weeks, 156 weeks, and every 24 weeks thereafter until the end of the study or closure of the physes.
 - **For roll-over patients**, imaging follow-up will be conducted around every 12 weeks in the following year after the MRI/x-ray considered as baseline for parent trial (when applicable) and around every 24 weeks thereafter until the end of the study or closure of the physes.MRIs (or x-rays) will be sent to central evaluation by radiology expert on a timely manner.
 - For patients aged 19 and older, bone imaging follow-up procedures will be performed around every 48 weeks (instead of around every 24 weeks) until the end of the study or closure of the physes.

- Follow-up dental examination will be planned in order to follow the frequency of around every 12 weeks for first year and around every 24 weeks thereafter, taking in account, for roll-over patients, the participation in the parent trial:
 - **For new patients**, follow-up will be conducted, if applicable, at 12 weeks, 24 weeks, 36 weeks, 52 weeks, 76 weeks, 104 weeks, 128 weeks, 156 weeks, and every 24 weeks thereafter until the end of the study.
 - **For roll-over patients**, follow-up will be conducted around every 12 weeks in the following year after the dental examination considered as baseline in parent trial (when applicable) and around every 24 weeks thereafter until the end of the study.
- Follow-up dental imaging will be planned in order to follow the frequency of around every 24 weeks for first year and around every 48 weeks thereafter, taking in account, for roll-over patients, the participation in the parent trial:

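### The treatment-interruption limit for bone imaging does not fit the 48-week schedule at age 19 and over, and one phrase in footnote 13 still allows pregnancy tests 4 to 6 weeks apart

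*Protocol*

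**What the plan says.** **Bone imaging.** Flow Chart footnote 21 tells readers near its start that additional information for patients aged 19 and older stands at its end. There it says: "For patients aged 19 and older, bone imaging follow-up procedures will be performed around every 48 weeks", in place of about every 24 weeks. Sections 5.2.5 and 6.2.2 repeat this.

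The next paragraph of footnote 21 applies to all patients. It says that "if the follow-up procedure cannot be conducted at least every 16 weeks (during the first year)/28 weeks (thereafter), the study treatment" must be interrupted after discussion with the sponsor. The only exception is the one-time alignment with clinic visits for roll-over patients.

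Appendix 10.9, which covers exceptional circumstances, repeats the 28-week trigger, also without an age exception. It labels the period *second year* where footnote 21 says *thereafter*.

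For new patients, footnote 21 sets the spacing between procedures at "always minimum of 10 weeks (during the first year)/22 weeks (thereafter) and always maximum of 16 weeks (during the first year)/28 weeks (thereafter"). Roll-over patients have the same figures. Section 5.2.5 places the spacing limit and the age rule next to each other: "always maximum 16 weeks (first year)/28 weeks (thereafter) from previous procedure. For patients aged 19 and older".

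**Pregnancy tests.** The first sentence of footnote 13 requires testing of all female patients every 4 weeks. A later sentence of the same footnote sets the home or local urine tests between visits at every 4-6 weeks, if applicable.

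**The concern.** A site with a patient aged 19 or older whose bone image is late needs to know when drug has to be interrupted. The schedule says 48 weeks. The only stated trigger says 28 weeks and is addressed to all patients. The age rule replaces the imaging frequency but does not say what happens to the limits attached to the old frequency. The imaging monitors a potential effect on growth plates, and the rule governs whether a patient stays on drug.

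On pregnancy tests, one sentence allows a longer gap than the rest of the protocol. Section 4.2.2.3 attributes a high teratogenic and embryotoxic potential to the drug, and the Flow Chart footnotes are where sites look up frequencies.

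**Working it through.** **Part 1: bone imaging**

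Step 1: set the schedules beside their limits. All figures are in weeks, from footnotes 21 and 23; the window is the roll-over window.

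| Procedure | Schedule | Window | Min / max spacing | Interruption trigger |
|---|---|---|---|---|
| Bone, first year | 12 | −2/+4 | 10 / 16 | 16 |
| Bone, thereafter | 24 | −2/+4 | 22 / 28 | 28 |
| Dental imaging, first year | 24 | −2/+4 | 22 / 28 | 28 |
| Dental imaging, thereafter | 48 | −2/+4 | 46 / 52 | 52 |
| Bone, age 19+ | 48 | none of its own | none of its own | none of its own |

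Step 2: see how the limits relate to the schedules. In each of the first four rows:

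- minimum = schedule − 2: 12 − 2 = 10; 24 − 2 = 22; 48 − 2 = 46
- maximum = trigger = schedule + 4: 12 + 4 = 16; 24 + 4 = 28; 48 + 4 = 52

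The protocol does not state this as a rule, but every complete row follows it. The age 19+ row is the only one with a schedule and no matching limits.

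Step 3: size of the mismatch if the 28-week figure applies at age 19+.

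- Nominal: 48 − 28 = 20 weeks.
- With a ±1 week window: 47 to 49 weeks, so 47 − 28 = 19 to 49 − 28 = 21 weeks over.
- With the −2/+4 window: 46 to 52 weeks, so 46 − 28 = 18 to 52 − 28 = 24 weeks over.

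Neither range overlaps 22 to 28 weeks. The windowed figures assume that the usual windows carry over to the 48-week schedule, which the protocol does not say, and that the previous image was on time.

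Step 4: the two possible readings.

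- The 28-week trigger applies to all patients, as written. It then contradicts the 48-week schedule.
- The age rule overrides the trigger. Then no interruption trigger is stated for these patients.

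Step 5: can such patients occur? Section 3.3.1 admits roll-over patients who became adults in the parent trial, and Section 3.1 lets patients stay until just before their 22nd birthday. A new patient just under 18 at Visit 2 would turn 19 after about a year, within the expected minimum treatment of 76 weeks (76 / 52 = 1.46 years). Follow-up imaging applies only while physes are open, and the documents give no count of such patients at 19 or older.

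**Part 2: pregnancy tests**

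| Place in the protocol | Interval |
|---|---|
| Footnote 13, first sentence | 4 weeks |
| Footnote 13, urine tests between visits | 4-6 weeks |
| Table 1.4.2:1, foetal harm | 4 weeks |
| Section 5.2.3 | 4 weeks |
| Table 5.2.3:1, urine test | 4 weeks |
| Section 6.2.2, diary check at treatment visits | 4 weeks |
| Section 6.2.2, intermediate tests | 4 weeks |
| Section 6.2.2, diary check at End of Treatment | 4 weeks |
| Appendix 10.9 | 4 weeks, with interruption if not met |

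Eight statements say 4 weeks. One phrase allows up to 6, which is 6 − 4 = 2 weeks longer.

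**The case against.** The strongest defence is that the age rule is specific and signposted. The pointer near the start of footnote 21 means that the spacing limits for new and roll-over patients are to be read subject to it. Section 5.2.5 gives the age rule directly after its 28-week limit. Table 1.4.2:1 gives only the 12/24-week schedule ("to respect the frequency of around every 12 weeks for first year and around every 24 weeks thereafter, taking in account, for roll-over patients"), but it refers to the footnotes and Section 5.2.5 for detail. This stands: it would be wrong to count each mention of 28 weeks as a separate contradiction. What remains is the interruption sentence, which comes after the age rule, is addressed to all patients and lists an exception that is not age, together with its counterpart in Appendix 10.9.

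A reader might also infer that every patient imaged on the 48-week schedule would have to come off drug. The documents do not support that. The rule acts when imaging cannot be conducted in time, which is not the same as imaging not yet due, and only after discussion with the sponsor. Footnote 21 and Section 5.2.5 also allow time points to be adapted case by case with the sponsor. That flexibility softens the problem but supplies no limit.

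On pregnancy tests, a reader might count one home test in a 12-week visit gap at 6-weekly spacing instead of two at 4-weekly spacing, and conclude that tests will be lost. This does not follow either: Section 6.2.2 has sites confirm 4-weekly testing from the diary card and re-instruct the patient if it was not done. The phrase looks like a leftover, and the description of Global Amendment 5 confirms that 4 weeks was intended for all countries. The point rests on the current text alone.

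**Conclusion.** Both inconsistencies are in the current text. They concern safety-monitoring rules; no stated calculation is wrong, and the primary endpoint and its analysis are unaffected.

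For bone imaging, the retained trigger is 20 weeks shorter than the schedule at age 19 and over. The protocol therefore either contradicts itself or has no trigger for this group. The practical reach is limited: the group is probably small and may be empty, and the sponsor is consulted before any interruption. For pregnancy tests, one phrase allows a gap 2 weeks longer than the eight other statements. No change in exposure or in the number of tests performed is claimed.

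**What to change.** 1. In the interruption sentence of footnote 21 and in Appendix 10.9, add an exception for bone imaging at age 19 and older once the 48-week schedule applies, for example 52 weeks. This is the limit already used for 48-weekly dental imaging. Appendix 10.9 covers bone imaging and dental examination in one sentence, so restrict the exception to bone imaging.
2. Align the 22/28-week minimum and maximum spacing in footnote 21 and Section 5.2.5 for the same patients, for example to 46/52 weeks. On-schedule intervals of 47 to 49 or 46 to 52 weeks would then comply. Leave the first-year limits unchanged.
3. In the same Appendix 10.9 sentence, replace *second year* with *thereafter*.
4. In footnote 13, replace 4-6 weeks with 4 weeks.

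The cost is wording at the next amendment and one decision by the sponsor and SMC to confirm the age 19+ limits. No visits, procedures or data are added.
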